4 RESEARCH METHODS

4.1 STUDY DESIGN

This is a European, multi-country, multicenter, retrospective, observational, longitudinal study to describe the demographic characteristics and clinical profiles of patients with HER2+ breast cancer who were treated with neratinib as an extended adjuvant therapy, in the context of the EAP in Europe. Eligible patients will be selected among those having received at least one dose of neratinib in this EAP, between August 01, 2017 and December 31, 2020 (the patient identification period). The decision to prescribe neratinib was taken prior to and independent of the proposal to select a patient into this study and all data will be retrospectively collected from the patients' medical charts.

The definitions of terms used to describe various phases of this study are as below:

Patient Identification Period: Time period eligibility for selection of patients who initiated neratinib treatment within the EAP in Europe, from August 01, 2017 until December 31, 2020.

 Pierre Fabre TEMP CQA 0092 V2.0 Owning site : CORPORATE QA	Template to use for writing Corporate document, except Corporate policy and form, WORD in english	Page 12/29
--	--	------------

Study Entry Date: The cut-off date until when the eligible patients' data as obtained from medical charts are abstracted for analysis in the study.

Index Date: The index date is defined as the date of neratinib initiation

Baseline Period: All relevant data available prior to the first dose of neratinib initiation (index date)

Follow-up period: The period starting from neratinib initiation within the EAP in Europe (index date) until data cut-off date (end of the study observation period). Patients will be censored at date of death, or among patients who did not die, the data cut-off date (end of the study observation period) or date of last visit, whichever occurs first. Patients will have variable follow-up time periods, depending on their index dates and last contact dates.

A study completion follow-up will be performed for all enrolled patients for whichever of the following cases that come first:

- a. At the end of the study observation period
- b. Upon study withdrawal
- c. After attempts to trace patients lost to follow-up
- d. Deceased patients

Study Observation Period: The overall study observation period includes the period from baseline till study entry date, and all available data for each patient will be collected until the end of the observation period

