7.5 Study Entry Date

The study entry date is defined as the cut-off date until when the eligible patients' data as obtained from medical charts are abstracted for analysis in the study. This date will be the same for all patients and corresponds to the date of first patient in, 05 July 2022.

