7.7 Follow-up Period

The follow-up period for each patient extends from index date to end of the study observation period. Patients' data collection will be censored at date of death, or among patients who did not die, at the

end of the study observation period or at the date of last visit, whichever occurs first. Patients will have variable follow-up periods length, depending on their index date and last contact date.

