7.8 End of Observation (EOB) Date

The end of observation (EOB) date is defined as the study entry date, date of death or date of last contact, whichever happens first.

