13.2 Time to Event Analysis

All time to event outcomes described in the subsections below will be summarized using the Kaplan-Meier method as described in section 8.2, for FAS and by subgroup EU label; Previous adjuvant or neoadjuvant therapy; Residual disease after neoadjuvant treatment; Prior trastuzumab-based regimen overall; and Prior trastuzumab-based regimen last treatment. (section 8.4)

Patients for whom the event did not occur or who are lost to follow-up, will be censored at the last recorded date that the patient is known to be alive. For patients alive at end of study will be considered the date of study entry, for patients who withdraw consent will be considered the date of consent withdrawal, for patients lost to follow-up will be considered the date of last contact, as collected in the eCRF.

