13.2.1 Invasive Disease-Free Survival

iDFS is defined as the time, in months, from neratinib treatment initiation (index date) to the first occurrence of an iDFS event. The iDFS events include:

- Invasive ipsilateral breast tumor recurrence,
- Invasive contralateral breast cancer,
- Local/regional invasive recurrence,
- Distant recurrence,
- Death from any cause

Table 4 Event and time details for iDFS

Event	Type	Events and censoring dates
Invasive disease recurrence	Uncensored	Date of first recurrence
Death (all causes)	Uncensored	Date of death
Loss to follow-up	Censored	Date of EOB (section 7.8)
Withdraw consent	Censored	Date of EOB (section 7.8)
No event	Censored	Date of EOB (section 7.8)

iDFS in months, will be calculated as follows:

- For patients who have an event:
 - $(Date\ of\ event - Index\ date + 1) / 30.4$
- For patients who do not have an event (censored):
 - $(Last\ available\ date - Index\ date + 1) / 30.4$

All recurrences and respective dates will be identified from the “First Breast Cancer Recurrence” page of the eCRF. Death and corresponding date will be identified from the “Survival Status” page of the eCRF.

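### SAP 13.2 text and Tables 4-7 give different censoring dates, and CNS cumulative incidence is estimated by Kaplan-Meier with deaths censored

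*SAP*

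**What the plan says.** **Censoring.** SAP 8.2 refers to 13.2 for the censoring rules. Section 13.2 first states a general rule: patients without an event "will be censored at the last recorded date that the patient is known to be alive". It then goes by category. The rule for survivors reads "For patients alive at end of study will be considered the date of study entry". Withdrawals get a separate rule, worded as "for patients who withdraw consent will be considered the date of consent withdrawal". The third category, loss to follow-up, takes the last contact.

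Tables 4 to 7 give one date for loss to follow-up, withdrawal and no event: "Date of EOB (section 7.8"). SAP 7.8 has EOB "defined as the study entry date, date of death or date of last contact, whichever happens first". The withdrawal date is not part of that definition.

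On the study entry date, SAP 7.5 says: "This date will be the same for all patients and corresponds to the date of first patient in, 05 July 2022". SAP 7.6 ends the observation period there. SAP 7.7 stops follow-up of surviving patients at the "end of the study observation period or at the date of last visit, whichever occurs first", and Protocol 4.1 at "the data cut-off date (end of the study observation period) or date of last visit, whichever occurs first". The list of changes from protocol in SAP 7.10 contains no change to censoring.

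**CNS metastasis.** SAP 8.2 and Protocol 4.7.3 assess cumulative incidence by Kaplan-Meier. Table 6 in SAP 13.2.3 censors deaths at the date of death and has no row for a non-CNS first distant recurrence. A sentence in SAP 8.2, placed after the optional Cox regression, assigns a Fine and Gray model to time to CNS metastasis and names disease recurrences as the competing risk. Protocol 4.7.3 had attached that model to overall survival.

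**The concern.** Two programmers could each follow this SAP and get different censoring times from the same data. One consequence is visible in the report itself. Length of follow-up in SAP 10 is computed to EOB, while the reverse Kaplan-Meier follow-up of SAP 8.2 could be computed to the dates in the 13.2 text. Crediting time in which events are not collected also counts unobserved time as event-free, which can only push iDFS, DDFS and OS upwards.

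For CNS metastasis, a patient who dies first can no longer have the event. Censoring that death and reporting one minus Kaplan-Meier estimates incidence as if death did not occur. This exceeds the share of patients who actually develop CNS metastasis.

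**Working it through.** **1. The rules side by side**

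| Patient | 13.2 text | Tables 4-7 | Do they differ? |
|---|---|---|---|
| Lost to follow-up | last contact | EOB | No, if last contact is on or before the cut-off |
| Alive, last contact on or after cut-off | 05 July 2022 | 05 July 2022 | No |
| Classed alive, recorded last contact before cut-off | 05 July 2022 | last contact | Yes |
| Consent withdrawn | withdrawal date | at most 05 July 2022 | Yes, if withdrawal is after the cut-off |

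An enrolled patient cannot withdraw before being enrolled, and nobody was enrolled before 05 July 2022. So a withdrawal date is on or after the cut-off.

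**2. Single patients.** The SAP formula is months = (date − index + 1)/30.4. The contact and withdrawal dates here are illustrations; index is 01 June 2020.
- Cut-off: 765/30.4 = 25.2 months.
- Classed alive, last contact 31 December 2021: 579/30.4 = 19.0 by the tables, 25.2 by the text.
- Withdrawal on 05 December 2022: 918/30.4 = 30.2 by the text, at most 25.2 by the tables.

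**3. Potential follow-up to the cut-off.** Index 31 December 2020 gives 552/30.4 = 18.2 months; index 01 August 2017 gives 1800/30.4 = 59.2 months. Every patient therefore passes the last tabulated time, 18 months, before the cut-off. Time credited after the cut-off to a withdrawn patient cannot change any rate tabulated at or before 18 months. It can change the tail of the curve, any quartile reached there, and the reverse Kaplan-Meier summary.

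**4. Patients classed alive with an earlier last contact.** The documents give no count, so the shares are assumptions: 5%, 10% or 25%, which is 6, 12 or 30 of the 120 patients in SAP 4.2. The simulation has 600,000 patients, potential follow-up uniform from 18.16 to 59.21 months, and an exponential iDFS hazard set to 93.9% at 24 months (the pivotal-trial figure in Protocol section 2). Events are known up to last contact only.

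| Last contact before cut-off | Reverse-KM median, text minus tables (months) | iDFS at 18 months, text minus tables (points) |
|---|---|---|
| 0-6 months | about 0.15, 0.3, 0.7 | 0.002, 0.003, 0.008 |
| 0-12 months | about 0.3, 0.6, 1.5 | 0.007, 0.014, 0.035 |

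For scale, iDFS at 18 months is 0.939^(18/24) = 0.954, and the 95% CI half-width at n = 120 is 1.96 × √(0.954 × 0.046/120), about 3.7 points.

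**5. CNS metastasis.** With constant hazards a (CNS) and d (death), 1−KM = 1 − exp(−at), and cumulative incidence = a/(a+d) × [1 − exp(−(a+d)t)]. The assumed ranges are a = 0.5-1% and d = 1-3% per year.

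| a, d per year | Time | 1−KM | Cumulative incidence | Excess (points) |
|---|---|---|---|---|
| 0.5%, 1% | 18 months | 0.747% | 0.742% | 0.006 |
| 1%, 3% | 18 months | 1.489% | 1.456% | 0.033 |
| 0.5%, 1% | 48 months | 1.980% | 1.941% | 0.039 |
| 1%, 3% | 48 months | 3.921% | 3.696% | 0.225 |

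**The case against.** The strongest reply is that the documents already settle most of this. Protocol 4.1 plans a completion follow-up for every enrolled patient, and SAP 10 reports survival status at study entry. A patient classed alive at the end should therefore normally be known alive at the cut-off, where EOB and study entry coincide. A patient who cannot be traced is lost to follow-up, where text and tables agree. SAP 7.6 and 7.7 end follow-up at study entry, so a sensible programmer would cap a later withdrawal date. SAP 8.2 does name a competing-risks model for CNS metastasis, and the bias at 18 months is far below one patient in 120 (0.83 points).

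Much of this stands. It limits the living-patient conflict to records where status and last-contact date disagree, and it shows which rule was probably intended. It does not remove the conflict: the withdrawal clause carries no cap, and the cap has to be inferred from other sections. The Fine and Gray sentence does not answer the CNS point either. It is a regression model, its link to the optional Cox analysis is unclear, it does not name death, and the planned descriptive estimate remains Kaplan-Meier.

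A reader might infer three stronger things that the documents do not support:
- **That living patients in general are wrongly censored.** The rules differ only in the narrow case above.
- **That contact stopped at 12 months, leaving years of unobserved time.** That is the last fixed timepoint in Protocol 4.4, but the same section adds later tumor assessment visits, and Protocol Table 1 collects recurrence and survival status to the end of observation.
- **That DDFS and CNS events are missed because SAP 13.2.2 and 13.2.3 take recurrences from the first-recurrence page.** The eCRF is not in the documents, so this cannot be judged.

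**Conclusion.** The point holds and is minor. The 13.2 text conflicts with Tables 4-7. The tables cannot run past the cut-off, and they agree with Protocol 4.1 and SAP 7.7 except that those say last visit where SAP 7.8 says last contact. The withdrawal clause is wrong as written, because any withdrawal after 05 July 2022 is credited with time outside the observation period. The conflict for patients classed alive is conditional, and its frequency is unknown.

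Under the assumptions shown, the censoring choice moves 18-month iDFS by less than 0.04 points and median follow-up by about 0.15 to 1.5 months. The CNS estimate is too high by 0.01-0.03 points at 18 months and 0.04-0.22 at 48 months, which is beyond the last tabulated time. The direction of the CNS bias is certain if any patient dies before CNS metastasis while others remain at risk and a CNS event follows; its size rests on the assumed hazards. No exploratory conclusion is likely to turn on either part. The case for acting is that the SAP should yield one answer from one dataset.

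**What to change.** - In SAP 13.2, delete the clauses that use study entry and the withdrawal date. Use EOB, capped at 05 July 2022, in the text, in Tables 4-7 and in the time formulas, which now refer to a last available date or a last date known alive. Kaplan-Meier, reverse Kaplan-Meier and the follow-up length in SAP 10 will then agree.
- State once whether the date that ends observation is the last visit (7.7) or the last contact (7.8), and whether a consent or non-opposition exchange counts.
- Estimate CNS cumulative incidence by Aalen-Johansen, with death and non-CNS first distant recurrence as competing events, both shown in Table 6. The second belongs there because it rules out CNS metastasis as first distant recurrence. Leaving those patients at risk to EOB does not in itself inflate the estimate.

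The cost is two deleted clauses, one clarified definition, two rows in Table 6, and small programming changes. No new data are needed.

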13.2.1 Invasive Disease-Free Survival

iDFS is defined as the time, in months, from neratinib treatment initiation (index date) to the first occurrence of an iDFS event. The iDFS events include:

- Invasive ipsilateral breast tumor recurrence,
- Invasive contralateral breast cancer,
- Local/regional invasive recurrence,
- Distant recurrence,
- Death from any cause

Table 4 Event and time details for iDFS

Event	Type	Events and censoring dates
Invasive disease recurrence	Uncensored	Date of first recurrence
Death (all causes)	Uncensored	Date of death
Loss to follow-up	Censored	Date of EOB (section 7.8)
Withdraw consent	Censored	Date of EOB (section 7.8)
No event	Censored	Date of EOB (section 7.8)

iDFS in months, will be calculated as follows:

- For patients who have an event:
 - $(Date\ of\ event - Index\ date + 1) / 30.4$
- For patients who do not have an event (censored):
 - $(Last\ available\ date - Index\ date + 1) / 30.4$

All recurrences and respective dates will be identified from the “First Breast Cancer Recurrence” page of the eCRF. Death and corresponding date will be identified from the “Survival Status” page of the eCRF.

13.2.2 Distant Disease-Free Survival

DDFS is defined as the time, in months, from neratinib treatment initiation (Index date) to the first distant tumor recurrence or death from any cause.

Table 5 Event and time details for DDFS

Event	Type	Events and censoring dates
Distant tumor recurrence	Uncensored	Date of first recurrence
Death (all causes)	Uncensored	Date of death
Loss to follow-up	Censored	Date of EOB (section 7.8)
Withdraw consent	Censored	Date of EOB (section 7.8)
No event	Censored	Date of EOB (section 7.8)

DDFS in months, will be calculated as follows:

- For patients who have an event:
 - $(Date\ of\ event - Index\ date + 1) / 30.4$
- For patients who do not have an event (censored):
 - $(Last\ available\ date - Index\ date + 1) / 30.4$

DDFS and respective date will be identified from the “First Breast Cancer Recurrence” page of the eCRF.

Document: ZZA65950_NEAR_SAP_v2.0

Author: [name]

Version Number: 2.0

Version Date: 22SEP2023

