4.3.3 Exploratory outcomes

Effectiveness will be evaluated only on HR+ patients based on the following outcomes, until the end of study observation period:

1. Characterization of first recurrence patterns (location, distribution, size, date)
2. iDFS, defined as the time from neratinib treatment initiation to:
 - a. First ipsilateral invasive breast cancer recurrence
 - b. First regional invasive breast cancer recurrence
 - c. First contralateral invasive breast cancer recurrence
 - d. First distant tumor recurrence
 - e. Death attributable to any cause.
3. DDFS, defined as the time from neratinib treatment initiation to the first distant tumor recurrence or death from any cause.
4. Incidence of CNS metastasis (either isolated or concurrent with other metastatic sites), defined as the time from neratinib initiation to CNS recurrence as first distant recurrence.
5. OS, defined as the time between neratinib treatment initiation (for early breast cancer) and death (due to any cause)

The following key data items will be collected for the **first three** clinical exploratory outcomes:

1. Recurrences after neratinib initiation: date of documented recurrence and site of recurrence, including size and distribution.
 - a. Invasive ipsilateral breast tumor recurrence
 - b. Invasive contralateral breast cancer
 - c. Local/regional invasive recurrence
 - d. Appearance / Occurrence of metastasis /Distant recurrence, including CNS metastasis
2. Date of death and cause of death (related to this cancer, non-breast cancer related, related to another cancer, related to neratinib, other, unknown)
3. Date of last patient visit during follow-up (if applicable)

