13.1 First Recurrence

The patterns of the first recurrence after neratinib initiation will be described based on frequencies and percentages of the following variables for HRAS by EU label and for FAS by Hormone receptor (section 8.4):

- Number and percentage of patients with a first recurrence. Percentage computed among HRAS.
- Number and percentage of patients by type of the recurrence: Invasive ipsilateral breast tumor recurrence (IIBTR), Invasive contralateral breast cancer recurrence (ICBCR), Regional invasive recurrence (RIR), Distant tumor recurrence (DTR) – or metastasis, Second breast cancer.
Percentage computed among HRAS.
 - Number and percentage of patients by site of recurrence. Percentage computed among HRAS with the type of recurrence:
 - IIBTR, ICBCR and RIR: Breast, Chest, Axillary lymph node(s), Skin, Nipple complex, Other
 - DTR or metastasis: Bone, Skin, Non-regional lymph node(s), Lung, Liver, CNS, Pleura, Adrenal glands, Ovary(ies), Left breast, Right breast, Other
 - If second breast cancer, the type: HR+, Triple negative, Other
- Number and percentage of patients with treatment administered for first recurrence
- Number of treatments by patient
- Treatment name: Trastuzumab, Pertuzumab, T-DM1, T-deruxtecan, Lapatinib, Tucatinib, Other
- Treatment duration (months), calculated as:
 - For discontinued treatment, $(End\ date - Start\ date + 1) / 30.4$
 - For ongoing treatment, $(EOB\ date - Start\ date + 1)$

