13.2.3 Time to Central Nervous System Metastasis

Time to CNS metastasis (either isolated or concurrent with other metastatic sites) is defined as the time, in months, from neratinib initiation (index date) to CNS metastasis as first distant recurrence.

Table 6 Event and time details for CNS metastasis

Event	Type	Events and censoring dates
CNS metastasis	Uncensored	Date of first recurrence
Death (all causes)	Censored	Date of death
Loss to follow-up	Censored	Date of EOB (section 7.8)
Withdraw consent	Censored	Date of EOB (section 7.8)
No event	Censored	Date of EOB (section 7.8)

Time to CNS metastasis in months, will be calculated as follows:

- For patients who have an event:
 - $(Date\ of\ event - Index\ date + 1) / 30.4$
- For patients who do not have an event (censored):
 - $(Last\ available\ date - Index\ date + 1) / 30.4$

CNS metastasis as first distant recurrence and respective date will be identified from the “First Breast Cancer Recurrence” page of the eCRF.

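### The source page and date rule for DDFS and CNS metastasis do not match the endpoints when a distant relapse follows a non-distant first recurrence

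*SAP*

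**What the plan says.** Protocol 4.3.3 gives "DDFS, defined as the time from neratinib treatment initiation to the first distant tumor recurrence or death from any cause". SAP 13.2.2 agrees: time runs from index "to the first distant tumor recurrence or death from any cause". In neither document does an earlier non-distant recurrence end the endpoint.

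The derivation is narrower. In SAP 13.2.2, "DDFS and respective date will be identified from the" First Breast Cancer Recurrence page, and Table 5 dates a distant recurrence at "Date of first recurrence". In SAP 13.2.3, "CNS metastasis as first distant recurrence and respective date will be identified from the" same page, and Table 6 uses the same date label.

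SAP 13.1 tabulates "Number and percentage of patients with a first recurrence" by type: ipsilateral, contralateral, regional, distant or second breast cancer. A first recurrence therefore need not be distant. Patients with no event are censored at EOB, and SAP 7.8 states: "The end of observation (EOB) date is defined as the study entry date, date of death or date of last contact, whichever happens first". No rule covers a non-distant recurrence that comes first.

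The data list in Protocol 4.3.3 is wider: "Recurrences after neratinib initiation: date of documented recurrence and site of recurrence, including size and distribution", with distant and CNS disease among the items. Protocol Table 1 schedules recurrence status to the end of the observation period. SAP 7.10, which lists changes from the protocol, mentions no narrowing.

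**The concern.** The endpoint asks when distant disease first appeared. The named source is a page about the first recurrence of any kind. The two coincide unless the first recurrence was ipsilateral, regional or contralateral and distant disease came later. For that patient the SAP gives no reliable route to the correct event and date.

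At stake are the DDFS curve and the CNS incidence. Both rest on few events, and SAP 13.2 also plans them by subgroup, so one or two misclassified patients can be visible. Deaths still enter DDFS under Table 5, so a missed distant relapse may reappear there late. Table 6 censors deaths, so a missed CNS event does not reappear.

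**Working it through.** The plan states no expected DDFS or CNS figure, so there is none to reproduce.

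**1. One patient through the SAP formula**, (date − index + 1)/30.4. The dates are illustrative: index 01 Jan 2019, local recurrence 01 Oct 2019, distant relapse 01 Jun 2020.

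- Local recurrence: (273 + 1)/30.4 = 9.0 months.
- Distant relapse: (517 + 1)/30.4 = 17.0 months. This is the DDFS event by definition.
- Single-entry page, patient alive at the 05 July 2022 cut-off (SAP 7.5): censored at (1281 + 1)/30.4 = 42.2 months.
- Single-entry page, death on 01 Sep 2021: event at (974 + 1)/30.4 = 32.1 months, 15 months late.
- Multi-entry page, Table 5 read literally: event at 9.0 months, 8 months early.
- If the relapse is in the CNS, a single-entry page gives no CNS event at all.

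**2. Which kind of page?** SAP 13.2.1 says that all recurrences and their dates come from this page, which would fit several entries. Against that, the page name and SAP 13.1 concern only the first recurrence. SAP Table 8 sets date rules variable by variable, and its only breast cancer recurrence date is that of the first; the other recurrence date listed is for AEs. The documents do not settle the question.

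**3. Size if the page holds one recurrence.**

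Inputs from the documents: 120 patients (SAP 4.2); index dates 01 August 2017 to 31 December 2020 (SAP 7.1), so potential follow-up is (551 + 1)/30.4 = 18.2 to (1799 + 1)/30.4 = 59.2 months; 2-year iDFS of 93.9% from the trial cited in Protocol section 2, so the hazard is −ln(0.939)/24 = 0.00262 per month, or 3.1% per year.

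Assumptions not in the documents: 20–40% of first events non-distant; later distant relapse at 5–30% per year; death after distant relapse at 25% per year; 5% of first events are deaths; index dates uniform; no loss to follow-up. The hazard is also doubled.

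Kaplan-Meier estimates from 1,000,000 simulated patients per scenario, scaled to 120, compare DDFS with every distant recurrence counted against DDFS with only distant first recurrences and deaths counted:

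| iDFS hazard | Non-distant share | Later distant relapse per year | Events, all counted | Events, single entry | Lost | Delayed to death | Shift at 18 / 36 / 48 months (points) |
|---|---|---|---|---|---|---|---|
| Base | 20% | 5% | 9.38 | 9.23 | 0.15 | 0.05 | 0.03 / 0.10 / 0.17 |
| Base | 20% | 30% | 10.10 | 9.46 | 0.64 | 0.24 | 0.17 / 0.47 / 0.71 |
| Base | 40% | 5% | 7.28 | 7.00 | 0.28 | 0.09 | 0.06 / 0.20 / 0.32 |
| Base | 40% | 30% | 8.66 | 7.37 | 1.29 | 0.46 | 0.32 / 0.96 / 1.45 |
| Twice | 20% | 5% | 17.78 | 17.50 | 0.28 | 0.09 | 0.06 / 0.20 / 0.31 |
| Twice | 20% | 30% | 19.07 | 17.84 | 1.23 | 0.45 | 0.31 / 0.93 / 1.36 |
| Twice | 40% | 5% | 13.84 | 13.27 | 0.56 | 0.19 | 0.12 / 0.40 / 0.63 |
| Twice | 40% | 30% | 16.45 | 14.00 | 2.45 | 0.89 | 0.62 / 1.86 / 2.71 |

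Every shift is upward. Within a scenario the lost share runs from 0.15/9.38 = 1.6% to 1.29/8.66 = 14.9%; at twice the hazard, from 0.28/17.78 = 1.6% to 2.45/16.45 = 14.9%.

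**4. Patients to query.** At mean potential follow-up of (18.2 + 59.2)/2 = 38.7 months, 120 × (1 − 0.939^(38.7/24)) = 11.6 first events. Of these, 20–40% is 2.3 to 4.6 patients. At twice the hazard, 120 × (1 − 0.939^(2 × 38.7/24)) = 22.0 events, hence 4.4 to 8.8 patients.

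**The case against.** The strongest reply is that the eCRF is not among the documents. The page may repeat, or may take a date for each recurrence type, as SAP 13.2.1 hints and the Protocol 4.3.3 data list would require. The date label in Table 5 sits in the row for distant recurrence, so a programmer may well read it as the first distant one. On that reading nothing is lost and only the wording needs tidying.

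This stands as a limit on what can be claimed. A reader might infer that DDFS is certainly biased upward and that later distant relapses are certainly treated as event-free. The documents support that only for a single-entry page; with several entries, the literal date rule errs in the other direction. It does not remove the point, because the text needs correction in both cases.

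A reader might also reason that one or two misses among 2 to 4 exposed patients would be 10–25% of DDFS events. That presumes that about half of those patients relapse distantly and are still alive at cut-off. The declared ranges give an expected loss of 1.6–14.9%.

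On CNS, both documents restrict the event to CNS disease as first distant recurrence. Leaving out CNS disease that follows other metastases is therefore by design. The gap is only CNS disease in the first distant relapse after a non-distant recurrence. SAP 8.2 mentions a Fine and Gray model for this endpoint, but in the context of a regression that depends on patient numbers. A model does not supply a missing event date.

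**Conclusion.** The point holds as a mismatch between endpoint and derivation, with the direction of error depending on an eCRF design that the documents do not show. A single-entry page makes DDFS too high and CNS incidence too low; a multi-entry page with the literal date rule puts events too early.

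The single-entry effect is small at 18 months, the last tabulated landmark (0.03 to 0.62 points). It grows to between 0.17 and 2.71 points at 48 months, and the curves, medians and quartiles use the full follow-up. These sizes rest on the assumed ranges above. The 120 is all patients: SAP 13 names the HR+ set and SAP 13.2 the FAS for these analyses, and the HR+ number is not given. With fewer patients the event counts shrink in proportion. The CNS effect was not sized.

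DDFS and CNS metastasis are exploratory. The primary objective is untouched, and iDFS is safe because the first invasive recurrence is all it needs. The correction should be made, but nothing central depends on it.

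**What to change.** In Tables 5 and 6, replace "Date of first recurrence" with the date of the first distant recurrence on or before the cut-off, whether or not a non-distant recurrence came first. For CNS, count the event only when the CNS is among the sites of that first distant recurrence. Taking the earliest CNS recurrence from any record would wrongly add CNS disease that follows other metastases. State which eCRF field or record supplies the date, and name the Survival Status page as the source of DDFS deaths, as SAP 13.2.1 already does for iDFS.

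Query the patients whose first recurrence was not distant: about 2 to 5 on the base assumptions, 4 to 9 at twice the hazard.

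If those dates cannot be obtained, relabel the endpoints as distant recurrence as first recurrence, or death (DDFS), and CNS recurrence as first recurrence. Report how many patients had a non-distant first recurrence, treat that recurrence as a competing event, and state the limitation.

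The cost is a small chart query plus somewhere to record the answers if the eCRF has no field. The fallback needs no new data but gives a narrower endpoint. Protocol 4.7.1 allows an SAP amendment before database lock; after lock, the change belongs in the report as a deviation.
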